4.2 PER PROTOCOL (PP)

The PP population is defined as subjects completing one year of treatment, without missing 10% or more of the assigned doses. Subjects with other major protocol violations/ deviations will be excluded.

A major protocol violation/deviation is defined as an action which would render the data incomparable due to compromising the effect of the study medication. A reason for

exclusion may include, but would not be limited to, taking contraindicated concomitant medications (CM). Subjects excluded from the PP analysis due to a major protocol violation/deviation will be identified in formal notes to file signed by the study director/medical monitor prior to data base lock.

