3.5.2 Stopping Rules

3.5.2.1 Individual Subjects

Subjects meeting individual Stopping Criteria will be withdrawn from the study. These include:

1. The Principal Investigator and/or Medical Monitor conclude it is unsafe for the subject to continue.
2. A new diagnosis of a significant medical condition or initiation of a new treatment if such a condition or the new treatment can influence the response to study drug (e.g., diabetes, renal failure).
3. Individual subjects with a change in HT-SDS ≤ 0 in the past 6 months may be withdrawn from treatment at the discretion of the PI and Medical Monitor.

For subjects with IGF-I SDS ≥ 3 , a repeat peak IGF-I sample should be obtained. For subjects with consecutive IGF-I SDS ≥ 3 , the PI and Medical Monitor will determine if the subject may proceed with a dose reduction or be removed from the study.

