5.4 Method of Assigning Subjects to Treatment Groups and Subject Number Assignments

Randomization into the study will be based on the order of appearance of subjects successfully completing screening activities with approval by the Medical Monitor. The randomization will be in a 3:1 ratio of somavaratan to daily rhGH, and be stratified by region, subject age and IGF-SDS to assure that the two treatments are not grossly imbalanced for factors that may influence treatment outcomes. A unique Subject Number will be sequentially assigned to each subject. (Table 2).

Table 2 Assignment of Subject Numbers

Cohort	Subject Numbers
Somavaratan	██████████
Daily rhGH	██████████

Note: All subject numbers may not be allocated.

To achieve the planned sample size for analysis, additional subjects will be enrolled as needed to account for subjects who withdraw prior to completing one month of treatment and Month 1 height evaluations. Subject numbers will not be re-assigned.

The statistician at the CRO will be responsible to implement the randomization. This is an open label study. Subjects, study sites, and the CRO will be informed of the treatment assignment, after randomization.

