6.4 HANDLING OF MISSING VALUES AND OUTLIERS

Because of subject privacy limitations, birth dates may only be reported by month and year in certain locations. Where the specific birth day is not available, the day of month will be imputed as the 15th.

For the primary endpoint in the ITT population, missing height at 12 months will be imputed from the last available height. This imputation assumes no growth after the last available measurement observed at study exit. This is an extremely conservative approach. For example, a █ year old █ subject who discontinued at month 6 with annualized HV of 6 cm/yr (Day 1 height of █ cm and Month 6 height of █) will have the height at 12 months imputed to █ cm, resulting in an annual HV of 3 cm/yr.

For the sensitivity analysis of the effect of missing data on the primary endpoint, height velocity at Month 12, a tipping point approach will be used. The missing data will be imputed as follows:

For the control group:

1. All subjects to the control group mean (calculated without subjects missing endpoint)
2. 50% to the group mean, 50% to the HV associated with each subjects last reported height (no additional gain in height)
3. Each subject's HV imputed based on its own last reported height

For the somavaratan group:

1. All subjects to the somavaratan group mean (calculated without subjects missing endpoint)
2. 50% to the group mean, 50% to the HV associated with each subjects last reported height (no additional gain in height)
3. Each subject's HV based on its own last reported height
4. Each subject imputed to HV based on last reported height, minus 1 cm.
5. Each subject imputed to HV based on last reported height, minus 2 cm (the non-inferiority margin, to avoid imputing to a common mean).

The reduction of the imputed HV by -1 and -2 cm will be limited to a minimum 0 HV, as negative HV is not possible. This will result in a total of 15 comparisons which should cover the range of plausible results for the subjects who are not able to provide Month 12 height velocity, and accounts for combinations where the somavaratan drop outs will have worse outcomes than drop outs in the control group (e.g., control group imputation 1 versus somavaratan imputations 2 to 5).

No imputations will be considered for the PP populations.

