6.11 EFFICACY ANALYSES

The primary efficacy analyses will be done using the All Randomized population, and will also be done using the mITT and PP populations.

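### The supportive per-protocol analysis can lose children because of their growth, and its discretionary exclusions are not decided under masking; if somavaratan is truly worse, this can move the result toward non-inferiority

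*SAP*

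**What the plan says.** SAP 4.2 sets two conditions for the PP set. The first is completion with adequate dosing: "The PP population is defined as subjects completing one year of treatment, without missing 10% or more of the assigned doses". The second is open: "Subjects with other major protocol violations/ deviations will be excluded". A major deviation is described as an action that compromises the effect of the study medication so far that the data can no longer be compared. One example is given (contraindicated concomitant medication) and the list is left open. These exclusions "will be identified in formal notes to file signed by the study director/medical monitor prior to data base lock". Protocol 9.3.4 has the completion, Month 12 assessment and 10% dose conditions but not the second ground, and SAP 6.2 does not list that ground among its four changes from the protocol.

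Protocol 3.5.2.1 says: "Individual subjects with a change in HT-SDS ≤ 0 in the past 6 months may be withdrawn from treatment". The decision is left to the principal investigator and the Medical Monitor. SAP 6.5.2 repeats the rule, which covers both arms.

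For missing data, SAP 6.4 says: "No imputations will be considered for the PP populations". SAP 6.11 runs the primary efficacy analyses on all randomized subjects and adds that they "will also be done using the mITT and PP populations". It does not say how a PP result that disagrees with the primary one will be read.

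On masking, Protocol 5.4 says: "Subjects, study sites, and the CRO will be informed of the treatment assignment, after randomization". SAP 6.5 blinds the sponsor and investigators to aggregate height velocity only. Neither document describes a masked review of PP exclusions.

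**The concern.** A PP set is meant to remove children whose data do not reflect the assigned treatment. A child who took every dose, grew poorly and was stopped under a protocol criterion has not deviated from the protocol, yet drops out of PP because of a measure closely tied to the primary endpoint. With no imputation in PP, that child's observed heights are not used there. The all-randomized analysis does the opposite: it keeps the same child and assumes no further growth.

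In a non-inferiority trial readers look to PP as a check on the all-randomized result. If the experimental arm has more poor responders, a completers-only set sheds more of them, and agreement between the two analyses reassures more than it should. The open-ended deviation ground adds a second route, because people who probably know the arm, and in the medical monitor's case individual growth, decide who is left out.

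**Working it through.** **Plan figures.** The documents give no figure for the size or bias of the PP set, so there is none to reproduce. The inputs taken from the plan are SD 3.0 cm/yr, margin 2.0 cm/yr and 57:19 subjects (SAP 3.5), and a control mean of 10 cm/yr, within the 9.5–11 of Protocol 1. As a check on the inputs, 76 subjects reproduces at one-sided 0.05 if 80% power is assumed (no power is stated): 3.0² × (1.645 + 0.842)² × (1 + 1/3) / 2.0² = 18.6, so 19 controls and 4 × 19 = 76.

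**Assumptions not in the plan.**
- True means are 8 (somavaratan) and 10 (daily rhGH), so the difference sits on the margin at −2.0.
- A height SDS change of zero or less is represented by an annual velocity below c = 4, 5 or 6 cm/yr.
- A fraction w of such children is withdrawn, equally in both arms.

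**Formula.** For an arm with mean μ and SD σ, let z = (c − μ)/σ and p = Φ(z), the share below the cut-off. The mean of those below is b = μ − σφ(z)/p. The mean of the children kept is (μ − w·p·b)/(1 − w·p).

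**Example, c = 5, w = 0.5.**
- Somavaratan: z = −1, p = 0.159, b = 8 − 3(0.242/0.1587) = 3.43. Kept mean = (8 − 0.5 × 0.1587 × 3.425)/(1 − 0.0793) = 8.39.
- Daily rhGH: z = −1.67, p = 0.048, b = 3.76. Kept mean = (10 − 0.5 × 0.0478 × 3.755)/(1 − 0.0239) = 10.15.
- PP difference = 8.39 − 10.15 = −1.76.

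**Results, SD 3.0.** The share of the whole trial withdrawn is w(3p_som + p_rhGH)/4.

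| Fraction withdrawn (w) | PP difference, c = 4 / 5 / 6 | Share of trial withdrawn |
|---|---|---|
| 0.25 | −1.91 / −1.89 / −1.87 | 1.9% / 3.3% / 5.3% |
| 0.5 | −1.82 / −1.76 / −1.71 | 3.7% / 6.5% / 10.6% |
| 1 | −1.62 / −1.45 / −1.26 | 7.4% / 13.1% / 21.2% |

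With SD 2.0 and w = 1, the range is −1.90 to −1.54.

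**Effect on the test.** The simulation used 40,000 trials per setting, 57:19, SD 3.0, cut-offs 5 and 6, and a pooled t-test at one-sided 0.025 without covariates. At a true difference of −2.0, PP falsely shows non-inferiority in 2.5% of trials with no selective withdrawal, about 3.6% at w = 0.25, 5.4–5.8% at w = 0.5 and 13–21% at w = 1.

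**Direction.**
- Equal true means, same w in both arms: p and b are the same in each arm, so the kept means are equal and the bias is 0.
- True difference −2.0, half the poor growers withdrawn in the somavaratan arm only: −1.61 to −1.45, false non-inferiority 8–11%.
- True difference −2.0, half withdrawn in the daily arm only: −2.15 to −2.26, false non-inferiority 1.0–1.4%. The bias reverses.

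**The case against.** A reader might infer that PP is bound to drift toward non-inferiority, or that the trial's main conclusion is at risk. The documents support neither.

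- Withdrawal is optional, applies to both arms and has no stated frequency. Drift toward non-inferiority needs somavaratan to be truly worse and the rule not to be used mainly in the daily arm.
- The 10% dose rule may push the other way. Protocol 1 describes poor compliance with daily injections as common and harmful to growth, so removing non-compliant daily-arm children could raise the control mean.
- The primary population is all randomized subjects (SAP 4.1). Withdrawn children stay in it with no further growth assumed, and 15 tipping-point combinations follow, some penalizing somavaratan alone by 1 or 2 cm (SAP 6.4). PP has no decision role in the SAP.
- The larger shifts strain the plan's own allowance of 8 drop-outs in 84 (9.5%) for all causes. Half use at a cut-off of 6, and full use at 5 or 6, would exceed it through poor-growth withdrawals alone.
- The model truncates full-year velocity, whereas the rule looks at height SDS over six months.

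A reader might also take it as stated that the signatories know the arm. Protocol 5.4 names subjects, sites and the CRO, not the study director or medical monitor. Their knowledge is a likely inference from the open-label design. That the medical monitor sees individual growth follows more firmly, from that role's part in the withdrawal decision. Poor growth is not in itself a deviation under SAP 4.2, and requiring completion is a conventional PP condition.

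All of this limits the size and certainty of the point. What stands is that the completion test can remove children because of growth, and that the discretionary ground is open-ended with no masked review.

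**Conclusion.** The point holds as a conditional weakness of a supportive analysis. If somavaratan is truly 2.0 cm/yr worse, SD is 3.0 and the withdrawal rule is used evenly, PP understates the deficit by about 0.09–0.13 cm/yr with a quarter of poor growers withdrawn, and by 0.18–0.29 with half. The upper end of the second range already needs more withdrawals than the planned drop-out allowance. These figures rest on the assumed 4–6 cm/yr cut-off and the assumed frequency of withdrawal. The effect of the discretionary exclusions cannot be quantified from the documents. This is a cheap improvement to make before database lock, so that PP can be read as a fair check on the primary result.

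**What to change.** In SAP 4.2, state that every exclusion for an other major deviation is decided before database lock from deviation listings with treatment arm and all height and growth data removed. Re-code the subject identifiers, since Protocol Table 2 allocates numbers by cohort, and remove product names and dose counts (24 versus 365) that would reveal the arm. Report all PP exclusions by arm and reason, with poor-growth withdrawals as their own category.

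Optionally, add a sensitivity run of PP that keeps every early stopper who took at least 90% of doses up to stopping, whatever the reason for stopping, using height velocity at the last on-treatment visit from the SAP 6.11.1 formula. This is preferable to changing the PP definition, and admitting all reasons avoids making entry depend on a recorded reason tied to outcome.

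The cost is SAP wording and a little listing work. Masking may be imperfect where the deviation itself points to one product. In the optional run, velocities annualized from a short interval are noisier and may run high. No change to the withdrawal rule is proposed.

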4.3 PHARMACOKINETICS/PHARMACODYNAMICS (PK/PD) POPULATION

The PK/PD population is defined as all subjects receiving study drug and having at least one post-treatment PK/PD assessment. A PK/PD per protocol subset will include all subjects with complete PK/PD assessments and no missed doses in the dosing interval prior to a PK/PD assessment.

4.4 SAFETY POPULATION

The safety population will consist of all subjects receiving any amount of study drug.

4.5 OTHER ANALYSIS POPULATIONS (INCLUDING SUBGROUPS)

Subjects entering puberty after one year will be grouped and analyzed.

Other populations and analyses may be conducted at the discretion of Versartis, Inc. to supplement the results or for research purposes.

4.6 TREATMENT MISALLOCATIONS

As this is an open-label study, should any treatment misallocations occur, all subjects will also be analyzed in the “As Treated” treatment group for the primary endpoint instead of “As Randomized.” A listing will be provided to display any subjects with treatment misallocations, should they occur.

4.7 PROTOCOL DEVIATIONS

All protocol deviations will be documented in the study files, and any significant deviations will be included in the study report. If any deviation is considered to have resulted in changes in treatment or data collected, separate analyses may be conducted to determine the impact of the deviation.

5. ENDPOINTS AND COVARIATES

5.1 PRIMARY ENDPOINTS

The primary efficacy endpoint for this study is annual height velocity (cm/yr) in the first year (12 months) of treatment and will be analyzed by a non-inferiority test of the somavaratan treatment height velocity compared to daily rhGH.

5.2 SECONDARY ENDPOINTS

The following secondary efficacy endpoints will be analyzed in hierarchical order:

- Change in height SDS (Height SDS based on Center for Disease Control (CDC) Clinical Growth Charts; 2000)
- Change in bone age relative to chronological age (BA/CA)
- Change in Body Mass Index
- Change in body weight

IGF-I and IGFBP-3 responses to study drug administration and their relationship to height velocity will be evaluated.

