9.6 Secondary Endpoints

The secondary efficacy endpoints are:

- Change in height SDS
- Change in bone age relative to chronological age (BA/CA)
- Change in Body Mass Index
- Change in body weight

- IGF-I and IGFBP-3 responses to study drug administration and their relationship to height velocity will be evaluated.

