6.2 CHANGES FROM PROTOCOL SPECIFIED ANALYSES

Changes to the protocol may result in changes to the planned analyses, and may change the defined analysis endpoints and methods. Any changes to analysis as a result of changes to the protocol will be documented as an amendment to this SAP. Other than transformations or modeling needed to address the structure and distribution of the resulting data, additional analyses will be for exploratory purposes only.

The changes from the protocol specified analyses are:

1. Growth Hormone Binding Protein (GHBP) and Acid Labile Subunits (ALS) will be summarized but not analyzed as secondary endpoints.
2. Inclusion of Levine's test for homogeneity of variance
3. Inclusion of Welch's t-test if there is unequal variance
4. Replaced multiple imputation for missing data with tipping point analysis

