6.3 STUDY HYPOTHESES

The primary comparison of the annualized height velocity between somavaratan and daily rhGH is based on the null hypothesis that the difference is less than or equal to -2.0 cm/yr, the non-inferiority margin.

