6.6 ADJUSTMENT FOR MULTIPLE COMPARISONS

Multiple comparisons of key endpoints are not planned. Any additional comparisons will be for exploratory purposes and definition of a significance level will not be done.

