6.11.2 Secondary Efficacy Endpoints

Secondary endpoints will be summarized with descriptive statistics, and as appropriate, comparisons with t-test or ANCOVA, or non-parametric methods if assumptions of normality are not met. Pubertal staging will be with categorical methods showing count and %. The change from baseline for the secondary endpoints will also be presented. For any comparisons performed, the null hypothesis for the test is that the two groups are equal at $p < 0.05$. There is no intent to show non-inferiority for the secondary endpoints, as the sample size was not determined to be sufficient to show non-inferiority for these secondary endpoints.

The main intent of ANCOVA will be to explore the influence of the covariates on the outcome of the secondary endpoint. Differences between treatment groups are not expected,

so there is no plan to adjust the alpha level of each comparison. The primary covariates will be those used for the primary endpoint, plus the baseline value of the secondary endpoint being analyzed.

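### Does the SAP's hierarchical order for the four secondary endpoints need a written gate and stop rule?

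*SAP*

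**What the plan says.** Four places in the SAP and one in the protocol bear on this.

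- **SAP 5.2** lists the four endpoints after the words "The following secondary efficacy endpoints will be analyzed in hierarchical order". The IGF-I and IGFBP-3 responses follow outside the ordered list.
- **SAP 6.11.2** gives the test. For any comparison performed, "the null hypothesis for the test is that the two groups are equal at" p < 0.05. It says that non-inferiority is not the aim for these endpoints, that ANCOVA serves mainly to explore covariates, and that no treatment differences are expected, "so there is no plan to adjust the alpha level of each comparison". It does not mention the order.
- **SAP 6.6** says "Multiple comparisons of key endpoints are not planned", and then "Any additional comparisons will be for exploratory purposes and definition of a significance level will not be done". It defines neither key endpoints nor additional comparisons.
- **SAP 6.3** covers the primary hypothesis only: "The primary comparison of the annualized height velocity between somavaratan and daily rhGH is based on the null hypothesis" that the difference lies at or below the margin of -2.0 cm/yr.
- **Protocol 9.6** opens its list with "The secondary efficacy endpoints are" and names the same four endpoints, plus the IGF responses, without a testing order. The protocol 9.1 sentence about not correcting for multiple comparisons concerns safety parameters, so it does not settle the matter.

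**The concern.** A hierarchy normally means a fixed sequence: each endpoint is tested at full alpha only if the one before it was significant, and usually only after the primary has succeeded. SAP 5.2 uses the word without the machinery, and the sections that should supply it never refer to the order.

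Take a BMI result with p < 0.05 after height SDS has failed. With 5.2 read as a fixed sequence, it cannot be claimed. Under 6.11.2 alone it is significant. Under 6.6, if the four endpoints count as additional comparisons, it has no significance level at all. The trial is open-label, and the blind in SAP 6.5 covers aggregate height velocity only, so BMI, weight and bone age data could be known before a reading is chosen. At stake would be the error rate of any secondary result presented as confirmatory on the strength of the hierarchy.

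**Working it through.** The documents state no familywise error for the secondary endpoints, so there is no figure of the plan's own to reproduce.

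**Inputs.** Four ordered endpoints (SAP 5.2). Each is tested for equality at 0.05 without adjustment (SAP 6.11.2), taken as two-sided because the null is equality. Assumptions: no true difference on any endpoint and jointly normal test statistics. The documents give no correlations, so a common correlation ρ is varied.

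**Familywise error, every test at 0.05.** If independent: 1 − 0.95⁴ = 1 − 0.8145 = 0.1855.

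**Fixed sequence.** Under the same null a false claim requires the first test to reject, so the error is 0.05 whatever the correlation.

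**Out-of-sequence significance.** This is the chance of a significant result after an earlier failure, which is what a stop rule would block. It equals 1 − Σ P(first m significant, the rest not), for m = 0 to 4. If independent:

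1 − (0.95⁴ + 0.05 × 0.95³ + 0.05² × 0.95² + 0.05³ × 0.95 + 0.05⁴)
= 1 − (0.81451 + 0.04287 + 0.00226 + 0.00012 + 0.00001) = 1 − 0.8598 = 0.140.

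For correlated statistics the same quantities come from numerical integration over one shared normal factor:

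| Assumed ρ | Familywise error, all at 0.05 | Significant after an earlier failure |
|---|---|---|
| 0 | 18.5% | 14.0% |
| 0.3 | 17.4% | 13.2% |
| 0.5 | 15.6% | 11.8% |
| 0.7 | 13.0% | 9.6% |
| 0.9 | 9.4% | 5.8% |

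**What a written sequence would deliver if no differences exist, as 6.11.2 expects.** It stops at height SDS in 95% of trials, ignoring the primary gate. Height SDS and height velocity use the same height measurements, so passing the gate shifts this slightly. With SD 3.0 cm/yr and 57 against 19 subjects, the standard error is 3.0 × √(1/57 + 1/19) = 0.795 cm/yr. Among trials passing a one-sided 0.025 gate, the sequence then stops at height SDS in 95.7%, 96.2% and 96.5% at assumed correlations of 0.5, 0.7 and 0.9 between the two statistics. With a one-sided 0.05 gate the figures are 95.8%, 96.4% and 96.9%.

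**Do the three sections conflict?** A fixed sequence spends the full 0.05 at each step, so 5.2 and 6.11.2 agree on the level; only stopping is unwritten. In 6.6, additional comparisons can be read as those beyond the ones the SAP specifies, much as SAP 6.2 calls additional analyses exploratory. On that reading 6.6 leaves the listed endpoints alone. If they are instead counted as additional, they are exploratory and support no claim.

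**The case for a change.** The best case for a change is that a testing order does nothing if every test runs at 0.05 regardless. The word therefore implies stopping, and a rule implied but not written can be chosen after the data are seen. Two sentences before database lock would close the gap, either by stating the sequence or by dropping the word and calling the p-values nominal.

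The textual part stands: no gate or stop rule is written anywhere, and no section says which reading prevails. The consequence is weaker. The error figures require a confirmatory secondary claim that neither document announces, together with no true difference on all four endpoints. The order itself is fixed in SAP 5.2, so a reader given the four p-values can apply the stop rule without further choices. The two remedies point in opposite directions, and choosing between them only records the sponsor's intention; neither corrects an analysis that would otherwise be wrong.

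A related clerical slip is also real. SAP 6.2 says "The changes from the protocol specified analyses are" and lists four, omitting the added order and the loss of the protocol 9.1 non-inferiority wording for growth and bone age endpoints other than height velocity. SAP 1 makes the SAP prevail over the protocol, so the omission leaves no doubt about which text governs. That list also omits the changed ITT definition, the added gender effect and the changed primary imputation. Those concern the primary analysis and are separate from this point.

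**Conclusion.** No change follows. The SAP leaves a stop rule unwritten for secondary comparisons that it treats largely as exploratory. It does state a significance level, 0.05 per comparison, and that level is compatible with the listed order. Analysts can report all four endpoints in that order with confidence intervals and nominal p-values and make no confirmatory claim from them.

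The exposure is conditional. Familywise error would be 18.5% if the tests are independent, and 9.4% to 17.4% at assumed common correlations of 0.9 down to 0.3, against 5% for a gated sequence. It arises only if a secondary result is presented as confirmatory and no true differences exist. The primary non-inferiority conclusion is the same under every reading. The view would change if the sponsor meant to rest a formal claim on a secondary endpoint; nothing in the protocol or SAP says so.
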